12 SAFETY ASSESSMENTS

Safety assessments (vital signs, AEs, SAEs, clinical laboratory results [routine hematology and biochemistry] are to be performed at protocol-specified visits, as specified in the Schedule of Assessments ([Table 1](#)).

12.1 Medical History

Medical history will be recorded at screening. Investigators should document the occurrence, signs, and symptoms of the subject's preexisting and currently ongoing conditions, including comorbid conditions, present at the time when informed consent is given and up to the time of first dosing (Day 1). Medical history will include alcohol consumption and smoking history, if applicable.

Illnesses first occurring or detected during the study and/or worsening of a concomitant illness during the study are to be documented as AEs on the eCRF in accordance with [Section 12.4](#). All changes not present at baseline or described in the past medical history and identified as clinically noteworthy must be recorded as AEs.

Additionally, demographic data will be collected for all subjects and include age, sex, race, and ethnicity.

Prior and concomitant medications are to be recorded on the eCRF. Refer to [Section 9.6.1](#) for details.

12.2 Vital Signs and Body Temperature – On-Site Visits

Vital signs (heart rate, systolic and diastolic blood pressure measurements, and SpO₂) and body temperature will be evaluated at the visits indicated in the Schedule of Assessments ([Table 1](#)). All vital signs will be measured after the subject has been resting in a sitting position for at least 5 minutes. Blood pressure measurements are to be taken in the same arm for the duration of the study. Body weight (without shoes) and height (without shoes) will be recorded at screening only.

Vital sign measurements will be repeated if clinically significant or machine/equipment errors occur. Out-of-range blood pressure or heart rate measurements will be repeated at the investigator's discretion.

12.3 Laboratory Assessments

Laboratory assessment samples ([Table 2](#)) to be obtained at designated visits as detailed in the Schedule of Assessments ([Table 1](#)).

Table 2. Laboratory Assessments

Hematology	Serum Chemistry	Pregnancy Test
Complete blood count: Hct Hb MCV Platelet count RBC count WBC count with differential	Albumin ALT ALP AST GGT BUN Sodium Potassium Chloride Carbon dioxide Creatinine Glucose Total bilirubin Direct bilirubin LDH CRP	A urine HCG pregnancy test will be performed on all women of childbearing potential at screening

Abbreviations: ALP = alkaline phosphatase; ALT = alanine aminotransferase; AST = aspartate aminotransferase; BUN = blood urea nitrogen; CRP = C-reactive protein; GGT = gamma-glutamyl transferase; HCG = human chorionic gonadotropin; Hb = hemoglobin; Hct = hematocrit; LDH = lactate dehydrogenase; MCV = mean corpuscular volume; RBC = red blood cell; WBC = white blood cell.

Blood will be analyzed at a central laboratory. A urine sample for pregnancy testing should be obtained for testing at the site using the provided test kits. All laboratory reports must be reviewed, signed, and dated by the investigator. A legible copy of all reports must be filed with the subject's electronic source documents for that visit. Clinically significant abnormal values occurring during the study will be followed up until repeat test results return to normal, stabilize, or are no longer clinically significant.

12.4 Adverse Events

12.4.1 Adverse Events

An AE is any symptom, physical sign, syndrome, or disease that either emerges during the study or, if present at screening, worsens during the study, regardless of the suspected cause of the event. All medical and psychiatric conditions (except those related to the indication under study) present at screening will be documented in the medical history eCRF. Changes in these conditions and new symptoms, physical signs, syndromes, or diseases should be noted on the AE eCRF during the rest of the study.

Subjects will be instructed to report AEs at each study visit. All AEs are to be followed up until resolution or a stable clinical endpoint is reached.

Each AE is to be documented on the eCRF with reference to date of onset, duration, frequency, severity, relationship to study drug, action taken with study drug, treatment of event, and outcome. Furthermore, each AE is to be classified as being serious or nonserious. Changes in AEs and resolution dates are to be documented on the eCRF.

For the purposes of this study, the period of observation for collection of AEs extends from the time the subject is administered study medication (Day 1) until Day 28 or early termination. Subjects with early termination will be followed up until Day 28. Follow-up of the AE, even after the date of therapy discontinuation, is required if the AE persists until the event resolves or stabilizes at a level acceptable to the investigator.

When changes in the intensity of an AE occur more frequently than once a day, the maximum intensity for the event should be noted. If the intensity category changes over a number of days, then those changes should be recorded separately (with distinct onset dates).

Specific guidelines for classifying AEs by intensity and relationship to study drug are given in [Table 3](#) and [Table 4](#).

Table 3. Classification of Adverse Events by Intensity

MILD: An event that is easily tolerated by the subject, causing minimal discomfort and not interfering with everyday activities.

MODERATE: An event that is sufficiently discomforting to interfere with normal everyday activities.

SEVERE: An event that prevents normal everyday activities.

Table 4. Classification of Adverse Events by Relationship to Study Drug


UNRELATED: This category applies to those AEs that are clearly and incontrovertibly due to extraneous causes (disease, environment, etc.).
 
UNLIKELY: This category applies to those AEs that are judged to be unrelated to the study drug but for which no extraneous cause may be found. An AE may be considered unlikely to be related to study drug if or when it meets 2 of the following criteria: (1) it does not follow a reasonable temporal sequence from administration of the study drug; (2) it could readily have been produced by the subject's clinical state, environmental or toxic factors, or other modes of therapy administered to the subject; (3) it does not follow a known pattern of response to the study drug; or (4) it does not reappear or worsen when the drug is readministered.
 
POSSIBLY: This category applies to those AEs for which a connection with the study drug administration appears unlikely but cannot be ruled out with certainty. An AE may be considered possibly related if or when it meets 2 of the following criteria: (1) it follows a reasonable temporal sequence from administration of the drug; (2) it could not readily have been produced by the subject's clinical state, environmental or toxic factors, or other modes of therapy administered to the subject; or (3) it follows a known pattern of response to the study drug.
 
PROBABLY: This category applies to those AEs that the investigator feels with a high degree of certainty are related to the study drug. An AE may be considered probably related if or when it meets 3 of the following criteria: (1) it follows a reasonable temporal sequence from administration of the drug; (2) it could not be reasonably explained by the known characteristics of the subject's clinical state, environmental or toxic factors, or other modes of therapy administered to the subject; (3) it disappears or decreases on cessation or reduction in dose (note that there are exceptions when an AE does not disappear upon discontinuation of the drug, yet drug-relatedness clearly exists; for example, as in bone marrow depression, fixed drug eruptions, or tardive dyskinesia); or (4) it follows a known pattern of response to the study drug.
 
DEFINITELY: This category applies to those AEs that the investigator feels are incontrovertibly related to study drug. An AE may be assigned an attribution of definitely related if or when it meets all of the following criteria: (1) it follows a reasonable temporal sequence from administration of the drug; (2) it could not be reasonably explained by the known characteristics of the subject's clinical state, environmental or toxic factors, or other modes of therapy administered to the subject; (3) it disappears or decreases on cessation or reduction in dose and recurs with reexposure to drug (if rechallenge occurs); and (4) it follows a known pattern of response to the study drug.


Abbreviation: AE = adverse event.

12.4.2 Serious Adverse Events

In general for any clinical trial an SAE is any untoward medical occurrence, in the view of either the investigator or Sponsor, that:

- results in death,
- is life-threatening,
- results in inpatient hospitalization or prolongation of existing hospitalization,
- results in persistent or significant disability/incapacity, and/or
- is a congenital anomaly/birth defect

For the purposes of this study, death and inpatient hospitalization will not be considered as an SAE, as the primary end point of this study is the proportion of subjects requiring COVID-19 related hospitalization (including emergency room visit) or who die due to any cause within 28 days of randomization

Other important non-COVID-19 medical events that may not be immediately life-threatening or result in death or hospitalization, based upon appropriate medical judgment, are considered SAEs if they are thought to jeopardize the subject and/or require medical or surgical intervention to prevent one of the outcomes defining an SAE. SAEs are critically important for the identification of significant safety problems; therefore, it is important to take into account both the investigator's and the Sponsor's assessment. If either the Sponsor or the investigator believes that an event is serious, the event must be considered serious and evaluated by the Sponsor for expedited reporting.

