12.4.3 Serious Adverse Event Reporting

An SAE occurring from the first dose administered until Day 28 must be reported to EVERSANA Pharmacovigilance and will be communicated to the Sponsor. Any such SAE due to any cause, whether or not related to the study drug, must be reported within 24 hours of occurrence or when the investigator becomes aware of the event. Notification can be made using the dedicated fax line or email for the EVERSANA Pharmacovigilance group:

EVERSANA Pharmacovigilance [contact]

EVERSANA Pharmacovigilance email address: [contact]

If the investigator contacts the EVERSANA Pharmacovigilance group by telephone, then a written report must follow within 24 hours and is to include a full description of the event and sequelae in the format detailed in the SAE reporting form.

EVERSANA Pharmacovigilance [contact]

The event must also be recorded on the standard AE eCRF. Preliminary reports of SAEs must be followed up by detailed descriptions later on, including clear and anonymized photocopies of hospital case reports, consultant reports, autopsy reports, and other documents when requested and applicable. SAE reports must be made whether or not the investigator considers the event to be related to the investigational drug.

Appropriate remedial measures should be taken to treat the SAE, and the response should be recorded. Clinical, laboratory, and diagnostic measures should be employed as needed in order to determine the etiology of the problem. The investigator must report all additional follow-up evaluations to the EVERSANA Pharmacovigilance group within 24 hours of becoming aware of the additional information or as soon as is practicable. All SAEs will be followed up until the investigator and Sponsor agree the event is satisfactorily resolved.

Any SAE that is not resolved by the end of the study or upon discontinuation of the subject's participation in the study is to be followed up until it either resolves, stabilizes, returns to baseline values (if a baseline value is available), or is shown to not be attributable to the study drug or procedures.

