12.4.4 Suspected Unexpected Serious Adverse Reactions

Adverse events that meet all of the following criteria will be classified as suspected unexpected serious adverse reactions (SUSARs) and reported to the appropriate regulatory authorities in accordance with applicable regulatory requirements for expedited reporting:

- serious
- unexpected (i.e., the event is not consistent with the safety information in the IB)
- there is at least a reasonable possibility that there is a causal relationship between the event and the study treatment

The investigator will assess whether an event is causally related to study treatment. The Sponsor (or EVERSANA) will consider the investigator's assessment and determine whether the event meets the criteria for being reportable as a 7-day or 15-day safety report. SUSARs that are life-threatening must be reported to the regulatory authorities and the institutional review board (IRBs; where required) within 7 days after the Sponsor (or EVERSANA) has first knowledge of them, with a follow-up report submitted within a further 8 calendar days. Other SUSARs must be reported to the relevant regulatory authorities and the IRBs within 15 calendar days after the Sponsor (or EVERSANA) first has knowledge of them.

The Sponsor (or EVERSANA) is responsible for reporting SUSARs and any other events required to be reported in an expedited manner to the regulatory authorities and for informing investigators of reportable events, in compliance with applicable regulatory requirements within specific timeframes. Investigators will notify the relevant IRBs of reportable events within the applicable timeframes.

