Adverse event causing study drug withdrawal	xxx	xx.x	xxx	xx.x
Adverse event causing discontinuation from study	xxx	xx.x	xxx	xx.x
Maximum severity for a subject ^c :				
Mild (Grade 1)	xxx	xx.x	xxx	xx.x
Moderate (Grade 2)	xxx	xx.x	xxx	xx.x

**DRAFT Table 14.3.1.1
Overall Summary of Adverse Events by Treatment
Safety Population**

	Camostat mesilate (N=xxx)		Placebo (N=xxx)	
	n	%	n	%
Severe (Grade 3)	xxx	xx.x	xxx	xx.x
Life-Threatening (Grade 4)	xxx	xx.x	xxx	xx.x
Death (Grade 5)	xxx	xx.x	xxx	xx.x
Notes: N=Number of subjects in the Safety Population; n=Number of subjects with the specified event. ^a A subject is only counted once in each row category. ^b A subject is counted once at the maximum severity observed over all treatment-emergent adverse events. Program: xxxxx.sas Database Lock Date: DDMMYYYY: Run Date: DDMMYYYY				

**DRAFT Table 14.3.1.2
Adverse Events Occurring in 5% of Subjects in Either Treatment Group by MedDRA System Organ Class and Preferred Term
Safety Population**

SOC	PT	Camostat mesilate (N=xxx)			Placebo (N=xxx)			All Subjects (N=X)		
		n	%	Events	n	%	Events	n	%	Events
Serious Adverse Events										
SOC1	PT1	xx	xx.x	xxx	xx	xx.x	xxx	xx	xx.x	xxx
...	...	xx	xx.x	xxx	xx	xx.x	xxx	xx	xx.x	xxx
Other (Non-serious) Adverse Events										
SOC1	PT1	xx	xx.x	xxx	xx	xx.x	xxx	xx	xx.x	xxx
...	...	xx	xx.x	xxx	xx	xx.x	xxx	xx	xx.x	xxx
N = number of subjects in the Safety Population. n = number of subjects reporting event. Events = total frequency of events reported. Program: xxxxx.sas Database Lock Date: DDMMMYYYY: Run Date: DDMMMYYYY										

Programming Notes:

Select all preferred terms/System organ classes where the % for any treatment group or overall is >= 5%. Sort preferred terms by descending order of frequency

DRAFT Table 14.3.1.3.1
Adverse Events Occurring in All Subjects by MedDRA System Organ Class and Preferred Term
Safety Population

MedDRA System Organ Class	MedDRA Preferred Term	Camostat mesilate (N=xxx)			Placebo (N=xxx)			All Subjects (N=X)		
		n	%	Events	n	%	Events	n	%	Events
Serious Adverse Events										
SOC1	PT1	xx	xx.x	xxx	xx	xx.x	xxx	xx	xx.x	xxx
...	...	xx	xx.x	xxx	xx	xx.x	xxx	xx	xx.x	xxx
Other (Non-serious) Adverse Events										
SOC1	PT1	xx	xx.x	xxx	xx	xx.x	xxx	xx	xx.x	xxx
...	...	xx	xx.x	xxx	xx	xx.x	xxx	xx	xx.x	xxx

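### The SAE exemption in protocol 12.4.2 covers inpatient admissions of any cause, but its stated reason covers only COVID-19 related ones, so prompt reporting of some non-COVID admissions rests on judgment

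*Protocol*

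**What the plan says.** Protocol 12.4.2 first lists the general SAE criteria, inpatient hospitalization among them. It then makes an exception for this trial: "For the purposes of this study, death and inpatient hospitalization will not be considered as an SAE". The reason given is that the primary endpoint is "the proportion of subjects requiring COVID-19 related hospitalization (including emergency room visit) or who die due to any cause within 28 days of randomization".

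Two routes based on judgment follow. Other important non-COVID medical events can be SAEs on medical judgment, and "If either the Sponsor or the investigator believes that an event is serious, the event must be considered serious". The criteria for life-threatening events, disability and congenital anomaly are not exempted.

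The consequences of seriousness are set elsewhere:

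- Protocol 12.4.1: "Furthermore, each AE is to be classified as being serious or nonserious".
- Protocol 12.4.3: an SAE "must be reported within 24 hours of occurrence or when the investigator becomes aware of the event", with detailed follow-up "including clear and anonymized photocopies of hospital case reports, consultant reports, autopsy reports" where requested and applicable.
- Protocol 12.4.4: seriousness is one of the criteria that must all be met for a SUSAR.
- SAP 4.3: AEs that lead to death or are life-threatening are recorded as SAEs in the datasets, and the SAE summaries are limited to non-COVID SAEs. Hospitalization is not named.
- SAP 3.1: any hospitalization or ER visit on the End of Study form is presumed COVID-related and counted as a primary endpoint failure. These subjects are to be described in the study report.
- SAP 5, shell Tables 14.3.1.2 and 14.3.1.3.1: AEs are split into serious events and "Other (Non-serious) Adverse Events".

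**The concern.** Leaving endpoint events out of SAE reporting is understandable, because they are counted anyway. That argument does not reach an admission for a cause other than COVID-19, and such an admission is one place where a serious drug reaction could first show.

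Safety is the secondary objective (protocol 6.1.2) and SAE incidence is a listed endpoint (6.2.2). No interim analysis is planned (13.5), so individual case reports carry weight while the trial runs. An unqualified exemption replaces an objective trigger with a judgment. Sites could then classify the same event differently, which would affect both prompt reporting and the SAE-incidence endpoint.

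**Working it through.** The plan has no figure of its own to reproduce. The main check sets the passages side by side.

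**Step 1: scope against reason (protocol 12.4.2).**

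| Event | Exempt from SAE status? | Covered by the stated reason? |
|---|---|---|
| COVID-19 related inpatient admission | Yes | Yes |
| Non-COVID inpatient admission | Yes | No |
| Death from any cause | Yes | Yes |

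Only the second row is mismatched.

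**Step 2: routes that remain for the second row.** The event is still an SAE if it is life-threatening, disabling, judged an important medical event, or believed serious by the investigator or the Sponsor. If none applies, it is nonserious under 12.4.1 and 12.4.2.

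**Step 3: what follows if none applies.** The automatic 24-hour report and SAE follow-up (12.4.3) do not start. The seriousness criterion for a SUSAR (12.4.4) is not met. The shell tables place the event with the non-serious AEs. SAP 4.3 does not restore it, since it names only fatal and life-threatening events.

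**Step 4: what is kept.** The event stays on the AE eCRF (12.4.1) and in the TEAE tables (SAP 4.3.1 to 4.3.3). If recorded on the End of Study form, it also counts in the primary endpoint and the subject is described in the study report (SAP 3.1).

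**Step 5: size.** The documents give no rate of non-COVID or drug-caused admission. Let r be an assumed risk of a drug-caused admission among n = 200 camostat subjects (planned number, protocol 13.1). Expected cases are 200r, and P(at least one) = 1 − (1 − r)^200.

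| r (assumed) | Expected | P(at least one) |
|---|---|---|
| 0.1% | 0.2 | 1 − 0.999^200 = 18% |
| 0.25% | 0.5 | 1 − 0.9975^200 = 39% |
| 0.5% | 1.0 | 1 − 0.995^200 = 63% |

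These are upper bounds for the gap, because r counts every drug-caused admission, including those that are serious by another route. If half were caught that way (also an assumption), r = 0.25% becomes 0.125%: expected 0.25, and 1 − 0.99875^200 = 22%.

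For scale, protocol 5.3 reports adverse reactions or events of any kind in 69/3806 = 1.8% and 57/4224 = 1.3% of subjects in other indications. The assumed r lies below both, but neither figure is an admission rate.

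**The case against.** The strongest objection is that the text already implies the narrower rule. After the exemption, 12.4.2 turns to other important non-COVID events that may not lead to death or hospitalization. This suggests that non-COVID events which do lead to admission are SAEs already. SAP 4.3 summarises non-COVID SAEs as a class, and 12.4.3 expects hospital records for SAEs. This stands as evidence of intent. It does not override an operative sentence without a qualifier, and a site following that sentence would be following the protocol. If the narrower rule was meant, stating it should be uncontroversial.

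The remaining safeguards are also real. Either the investigator or the Sponsor can make an event serious, and many worrying admissions would meet another criterion. Protocol 12.4.4 makes the Sponsor responsible for any other event that must be reported in an expedited manner. Platelets, liver enzymes and potassium are measured at Day 15, and the investigator must review every laboratory report (12.3). These narrow the gap but do not close it, because the site's 24-hour instruction in 12.4.3 is tied to SAEs.

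A reader might infer more than the documents support:

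- **That non-COVID admissions vanish from the data.** They do not; see Step 4.
- **That deaths are visible only inside the composite.** Survival to Days 15 and 28 is tabulated by arm (SAP 4.2.1, Tables 14.2.2.1 to 14.2.2.3). The AE summary has rows for fatal outcome and Grade 5, and there is a listing of deaths. Only admissions lack a table of their own.
- **That the mention of autopsy reports in 12.4.3 shows deaths were meant to be SAEs.** It fits equally well with a life-threatening SAE that later proves fatal.
- **That Study NI03-001 (protocol 5.2.2) gives a rate.** All six SAEs there, in three subjects, required hospitalization. All were judged unrelated to study drug and all but one came after the last treatment. This shows only that SAEs can be admissions.

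**Conclusion.** The concern holds as a mismatch between a rule and its reason. Protocol 12.4.2 exempts all inpatient admissions, while its reason justifies exempting only COVID-19 related ones. As written, prompt reporting and SAE classification of some non-COVID admissions depend on judgment instead of an automatic trigger.

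The number affected is probably small. Under an assumed drug-caused admission risk of 0.1% to 0.5%, the 18% to 63% chance of at least one case is a ceiling. The textual finding does not depend on these figures. The primary test, its error rate and its power are unaffected.

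A smaller point concerns deaths. There the reason is as wide as the exemption, but 12.4.2 says death is not an SAE while SAP 4.3 records AEs leading to death as SAEs. The precedence clauses (protocol 13, SAP 1) settle this for analysis coding but do not tell sites what to report within 24 hours.

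Rating: should be fixed.

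**What to change.** 1. In protocol 12.4.2, limit the hospitalization exemption to COVID-19 related admissions, so that it matches its stated reason. Other admissions then keep SAE status and the 24-hour report.
2. In the SAP, state that the COVID presumption in 3.1 applies to the primary endpoint only, as its wording already suggests. Carried into safety, it would label every admission COVID-related and so take it out of the SAE summaries, which SAP 4.3 limits to non-COVID events.
3. Minor: reconcile protocol 12.4.2 and 12.4.3 with SAP 4.3 on how fatal events are classified and what sites report.
4. Optional: one table of admissions by arm and recorded attribution.

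The cost is a few sentences plus SAE forms for non-COVID admissions. At an assumed risk of 0.5%, 1% or 2% in 300 subjects, that is 300 × 0.005 = 1.5, 300 × 0.01 = 3 or 300 × 0.02 = 6 admissions.
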